Study Number:	GCO#1: 16-1314

A minimum of 3 and a maximum of 6 subjects within a dose level must be observed for one cycle (90 day post EBRT completion) before accrual to the next higher dose level may begin.

Three patients within a dose level must be observed for one cycle (30 days post EBRT) before accrual to the next higher dose level may begin. The treatment for this study is RP + Civasheet implant + adjuvant EBRT for patients with high-risk or intermediate (non-clinically localized) prostate cancer with adverse pathologic features including seminal vesicle invasion, extra prostatic extension or a positive surgical margin. Since the clinical guidelines recommend adjuvant EBRT post RP only for patients with adverse pathologic features at RP, patients without these adverse pathologic features at RP will be replaced with additional patients at that dose level. Since however eligibility criteria is for high risk or non-clinically localized intermediate risk prostate cancer, the anticipated number of patients without these adverse pathologic features who will not receive adjuvant EBRT is 2 or less. While toxicities among these patients will be monitored according to the protocol, toxicities among these patients will not be used in determinations of the MTD. The MTD will only be determined for patients undergoing RP + Civasheet implant + adjuvant EBRT.

If a subject is withdrawn from the study prior to completing the entire cycle of therapy or prior to completing the entire DLT window without experiencing a DLT prior to withdrawal, an additional subject may be added to that dose level. Subjects missing doses due to a DLT will not be replaced since these subjects will be considered to have experienced a dose limiting toxicity.

d) Study Timelines:

The duration of an individual subject's participation in this study including follow-up is 5 years.

The expected duration for the investigators to complete this ranges between 1 month for a minimum of 1 subject and 44 months for a maximum of 12 subjects.

Table 1. Time and events table for those undergoing RP + Civasheet implant + adjuvant EBRT.

[Type here]

Effective Date: 10/18/2022

End Date: 10/17/2023

Protocol Title:	A Phase I Single-Arm Open Label Dose-Escalation Study of CivaSheet with Radical Prostatectomy with or without Adjuvant External Beam Radiation Therapy in Patients with High Risk Prostate Cancer									
Principal Investigator Name/Contact Info:	[name]/ [contact]/ [contact]									

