90 Days after Completion of EBRT

- Assessment of cumulative DLT's to decide whether progression to next dose or termination of study is necessary.

Follow-Up:

- Subjects will be followed every 6 months after completion of study treatment for 4 years or if the subject withdraws consent from participation, the subject will not be followed-up. Subjects may be followed-up by telephone or contacted by phone to schedule Mount Sinai office visits to monitor for cancer recurrence and or cancer progression in addition to late toxicity.
- Subjects will be followed yearly after completion of study treatment for 4 years or if the subject withdraws consent from participation, the subject will not be followed-up. Subjects may be followed- up by telephone or contacted by phone to schedule Mount Sinai office visits to monitor for cancer recurrence and or cancer progression in addition to late toxicity.
- If patients are not scheduled for their follow-up visits with Mount Sinai Health System, the study team will call the patient to schedule a visit.
 - If the patient schedules a follow-up at Mount Sinai, appropriate measures will be assessed according to the protocol and data will be recorded.
- If the patient is seeing a physician outside of Mount Sinai Health System, we will request that their labs and physician notes are sent to us.
 - A research coordinator will review and record the outside labs and contact the patients to collect any missing information that can be obtained by phone (i.e. bleeding, incontinence, etc.)
 - A symptomology follow-up form, as well as an IIEF assessment form are attached.
 - If additional information is necessary to assess DLTs or AEs, a coordinator will call the patient and request they schedule a follow up visit at Mount Sinai. If the patient is unable to come in for a follow-up visit, they will be dropped the study.
 - If patients are not responsive after 2 attempts, they will be considered lost to follow up and replaced.

For those with adverse pathologic features: At 1 week post RP+ Civasheet

[Type here]

Protocol Title:	A Phase I Single-Arm Open Label Dose-Escalation Study of CivaSheet with Radical Prostatectomy with or without Adjuvant External Beam Radiation Therapy in Patients with High Risk Prostate Cancer
Principal Investigator Name/Contact Info:	[name]/ [contact]/ [contact]
Primary Contact Name/Contact Info	[contact] [name]
Date Revised:	7/22/2022
Study Number:	GCO#1: 16-1314

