implant, 6 weeks after EBRT, 3 months after EBRT and 6 months after EBRT during the clinic visits, subjects will complete the IIEF to assess baseline erectile function following treatment. Subjects will undergo PSA testing for each follow-up visit. Those without adverse pathologic features not undergoing adjuvant EBRT will complete the IIEF to assess baseline erectile function following treatment and will also undergo PSA testing for each follow-up visit. Also at each follow-up visit or telephone follow up, subjects will be screened for toxicity and complications. The assessments may be done by phone when possible or lab results may be sent by the patient to our EMR if patient has followed up with an outside physician. For all patients, a CT-scan at day 0 (RP+Civasheet implant) will be done for a baseline stability assessment of the Civasheet. For all patients, a one month post-implant CT scan will be done of the pelvis for three purposes. The first purpose will be to perform a post-implant dosimetric analysis of the implanted Civasheet®. The bladder, rectum and any other identifiable structures (small bowel, large bowel or lymph nodes) will be outlined. The delivered dose will be calculated using a dose volume histogram and recorded. The second part of the CT will be to design the post-implant external beam radiation field among those who will undergo adjuvant EBRT. The third part will be to assess the stability of the Civasheet and any changes in position from initial implant. Among those who will undergo adjuvant EBRT, an additional post-implant CT scan at 90 days and 6 months will be done of the pelvis to prove stability of the device/implant method and to assess for cancer recurrence while those not undergoing adjuvant EBRT will not receive this imaging at 90 days and 6 months.

e) Specimen Banking for Future Uses Not Part of This Project:

NA

f) Data Storage, Transmission and Confidentiality:

To ensure data accuracy and completeness, random checks will be done by members of the research team listed in the protocol who are not directly responsible for data collection and entry. Data irregularities and errors will be collected and reported to the . Data collected and stored for current and future research use will include age, gender, [type here]

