While all genitourinary and gastrointestinal toxicities according to the NCI-CTCAE will be documented and evaluated every time a subject is seen Grade 3-5 hematuria, urinary retention and rectal bleeding/radiation proctitis are the specific toxicities used for dose escalation procedures. This study defines DLT as the development of NCI-CTCAE Grade >3 urinary retention, Grade 3 hematuria or Grade 3 rectal bleeding/radiation proctitis within 90 days post EBRT which is given 6 weeks after RP + Civasheet implant for 5 weeks. Grade 3 hematuria according to the NCI-CTCAE is defined as gross hematuria with indications including transfusion, IV medications, hospitalization, elective endoscopic, radiologic or operative intervention and limiting self-care activities for daily living. Grade 3 urinary retention is defined as an incomplete ability to empty the bladder with indications including elective operation or radiologic intervention, substantial loss of affected kidney function or development of mass. Grade 3 rectal bleeding/proctitis is defined as severe symptoms; fecal urgency or stool incontinence and limiting self-care activities for daily living. If > 33% of subjects experience these DLT at any dose, the dose level below that level will be considered the MTD. If  $\geq 33\%$  subjects experience a DLT at 60 Gy, the trial will be closed and no additional subjects will be enrolled. Also, if the first subject enrolled at 60 Gy experiences NCI-CTCAE Grade 4 or higher hematuria, fistula formation or proctitis, no additional subjects will be enrolled and the trial will be closed. If the first subject enrolled at 75 Gy experiences Grade 4 or higher hematuria, fistula formation or proctitis, no additional subjects will be enrolled at 75 Gy and 60 Gy will be considered the MTD. Grade 4 hematuria is defined as hematuria with life-threatening consequences and urgent radiologic or operative intervention indicated. Grade 4 or higher fistula (anal or urinary) formation is defined as a fistula with life-threatening consequences with urgent radiologic or operative intervention indicated. Grade 4 or higher proctitis is defined as proctitis with life-threatening consequences and urgent intervention indicated. The time frame for DLT evaluation is the first 90 days after EBRT. EBRT is given 6 weeks after RP+ Civasheet implant at 45 Gy in 25 fractions (Monday-Friday for 5 weeks). If > 33 % of subjects experience DLT at any dose level, the dose level below that level will be

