considered the MTD. Or if the highest level (75 Gy) has been reached and < 33% of subjects have experienced DLT, 75 Gy will be considered the MTD. If in the first subject treated at 75 Gy, NCI-CTCAE Grade 4 or higher hematuria, prostatitis or fistula formation occur, no additional subjects will be enrolled at 75 Gy and 60 Gy will be considered the MTD.

**Secondary:** We will describe the adverse events, toxicity and complication profile associated with Civasheet overall and at each dose when administered with RP and EBRT and also separately for those not receiving EBRT. Overall and for 60 and 75 Gy, the toxicity and complication profile associated with the Civasheet® will be assessed. Rates for surgical complications and adverse events, acute (< 90 days) and late (18 months days) GU and GI toxicity and adverse events using the NCI-CTCAE v4.0, RTOG Acute Toxicity Scale and Late Radiation Morbidity scales will be assessed. Erectile preservation and total urinary incontinence will be assessed overall and for each dose group once all subjects have completed the 6 month follow-up after EBRT. Peri- and post-operative complications associated with surgery will be assessed and graded using the Clavien-Dindo classification of surgical complications. Erectile preservation rates [IIEF score (erectile component) > 18] will be assessed, continence defined as the use of no pads will also be assessed. Binary or categorical outcomes will be described with proportion and 95% confidence intervals and continuous measures will be summarized with mean (SD) or median (IQR), as appropriate.

BCR defined as a post-prostatectomy serum PSA > 0.2 ng/ml will also be assessed for each subject. To evaluate cancer control, the Kaplan Meier-Method will be used to estimate BCR overall and for each dose group and separately for those receiving vs. not receiving EBRT once all subjects have completed the 6 months follow-up after EBRT or 6 months follow-up after Civasheet implant if no EBRT is given.

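### The SAP plans one Kaplan-Meier analysis of BCR, at a 6-month trigger, and none after the 4-year follow-up, so by-dose follow-up is unequal and short at 75 Gy

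*SAP*

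**What the plan says.** The SAP, under Secondary, defines the event and gives it no time limit: "BCR defined as a post-prostatectomy serum PSA > 0.2 ng/ml will also be assessed for each subject". On the method, the SAP says that "the Kaplan Meier-Method will be used to estimate BCR overall and for each dose group", with a further split by whether EBRT was received. The timing is "once all subjects have completed the 6 months follow-up after EBRT or 6 months follow-up after Civasheet implant if no EBRT is given". No other BCR analysis time appears in either document.

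The protocol's Follow-Up text reads "Subjects will be followed every 6 months after completion of study treatment for 4 years"; a parallel bullet says yearly, also for 4 years. The stated purpose is "to monitor for cancer recurrence and or cancer progression in addition to late toxicity". The text after the Follow-Up bullets adds "Subjects will undergo PSA testing for each follow-up visit". Study Timelines states: "The duration of an individual subject's participation in this study including follow-up is 5 years".

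The two Withdrawal of Subjects sections mention an analysis of subjects who completed the study alongside an intent-to-treat analysis. They name no endpoint, method or time.

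**The concern.** Cancer control is the question that the BCR endpoint is meant to answer. The trial plans years of follow-up that bear on it, but the one analysis named in the SAP is triggered by the last subject reaching 6 months.

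Dose levels are filled in sequence, so the last-treated subjects are all in the higher dose group. A calendar cut therefore gives the two groups very different follow-up, and it is shortest at 75 Gy. What is at stake is whether the by-dose curves can say anything about recurrence beyond the first year or so at 75 Gy. Dose selection does not depend on it.

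**Working it through.** **Inputs**
- Cohorts of 1, 2 and 3 subjects at 60 Gy, then 1, 2 and 3 at 75 Gy, each opened when the previous DLT window closes (Protocol, Number of Subjects).
- Implant to end of EBRT: 6 + 5 = 11 weeks = 77 days = 2.53 months (SAP, Primary Outcome).
- DLT window: 90 days = 2.96 months. One cycle = 77 + 90 = 167 days = 5.49 months.
- Planned follow-up: 48 months, counted here from the end of EBRT.
- Stated maximum duration for 12 subjects: 44 months (Protocol, Study Timelines).

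**Assumptions:** a full 12-subject trial, simultaneous entry within each cohort, no replacements.

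**The plan's own figure.** Six cycles give 6 × 5.49 = 32.9 months. Five cycles plus EBRT plus 6 months give 5 × 5.49 + 2.53 + 6 = 36.0 months. Neither is 44. Reaching 44 needs a cohort spacing of (44 − 2.53 − 6)/5 = 7.09 months if 44 is the BCR cut, or (44 − 5.49)/5 = 7.70 months if 44 is the end of the last DLT window. That is about 1.6 to 2.2 months more per cohort, an accrual lag that the documents do not state. I do not call 44 wrong; it serves as the slower anchor.

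**Follow-up at the cut.** With spacing s, cohort j (1 to 6) has 6 + (6 − j) × s months after EBRT.

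| Schedule | s | Cut (months from first implant) | 60 Gy cohorts | 75 Gy cohorts | Mean 60 Gy | Mean 75 Gy | Mean all |
|---|---|---|---|---|---|---|---|
| A: no lag | 5.49 | 36.0 | 33.4, 27.9, 22.5 | 17.0, 11.5, 6.0 | 26.1 | 9.7 | 17.9 |
| B: 44 = cut | 7.09 | 44.0 | 41.5, 34.4, 27.3 | 20.2, 13.1, 6.0 | 32.0 | 10.7 | 21.4 |
| C: 44 = end of last DLT window | 7.70 | 47.0 | 44.5, 36.8, 29.1 | 21.4, 13.7, 6.0 | 34.2 | 11.1 | 22.7 |

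Means are weighted by cohort size, for example A at 75 Gy: (1 × 17.0 + 2 × 11.5 + 3 × 6.0)/6 = 9.7.

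**Share of the 48 months falling after the cut**
- All subjects: 1 − 17.9/48 = 63% (A), 1 − 21.4/48 = 55.5% (B), 1 − 22.7/48 = 53% (C).
- 75 Gy: 1 − 9.7/48 = 80% (A) to 1 − 11.1/48 = 77% (C).
- 60 Gy: 26.1/48 = 54% (A) to 34.2/48 = 71% (C) would be analysed.

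**Counted from prostatectomy** (add 2.53 months), the longest-followed 75 Gy subject is at 19.5, 22.7 or 23.9 months under A, B or C. The shortest-followed 60 Gy subjects are at 25.0, 29.8 or 31.6 months. So every 60 Gy subject, and no 75 Gy subject, has reached 24 months. At 75 Gy at most 3 of 6 remain at risk beyond 6 months after EBRT, and at most 1 beyond 11.5 to 13.7 months.

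**Sensitivity.** The 24-month statement fails once s exceeds (24 − 6 − 2.53)/2 = 7.74 months, only just above schedule C. Mean overall follow-up is 6 + (26/12) × s, where 26 = 5×1 + 4×2 + 3×3 + 2×1 + 1×2 + 0×3. It reaches 24 months, half of 48, at s = 8.3. If the trial stops after six subjects at 60 Gy with no lag, those cohorts have 17.0, 11.5 and 6.0 months: mean 9.7, with 80% after the cut.

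**With a final analysis.** Full follow-up is 12 × 48 = 576 person-months. The planned cut uses 12 × 17.9 = 215 to 12 × 22.7 = 272, of which 58 to 67 of 288 at 75 Gy. The final analysis would fall at month 5 × 5.49 + 2.53 + 48 = 78 to 5 × 7.70 + 2.53 + 48 = 89.

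**The case against.** The best defence is that the plan reports at study completion by design. Table 1 has its last visit before long-term follow-up at week 35, about 6 months after EBRT ends, and describes the next 4 years as routine follow-up after the study. The protocol uses the same 6-month point for its toxicity summary. On that reading a later BCR report is an extra. This is a coherent account of the timing, but it does not explain why recurrence monitoring is planned within each subject's 5-year participation and then given no analysis.

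Several stronger readings are tempting, and the documents do not support them:
- **That the later data will never be analysed.** This would be inferred from silence. BCR is to be assessed for each subject without a time limit, and a completer analysis is mentioned, though too vaguely to fill the gap. What can be said is that no later BCR analysis is specified.
- **That each subject is censored at 6 months.** The trigger is a calendar date, and the first 60 Gy subject would contribute 33 to 45 months.
- **That the dose curves can be compared only to 6 months.** Kaplan-Meier handles staggered censoring; the 75 Gy curve continues with few at risk.
- **That most follow-up is lost at both doses.** At 60 Gy, in a full trial, more than half is analysed.

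Two further points stand. The long-term PSA data are less secure than they seem: in the text as read from the PDF, Table 1 shows no PSA in the 4-year column, whereas Table 2 does, and visits may be by telephone or rely on outside laboratories. And precision would stay poor: 1 event in 6 has an exact 95% interval of about 0.4% to 64%.

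**Conclusion.** The point holds as a gap in the analysis plan with a cheap remedy. One BCR analysis is specified, at the 6-month trigger, and none uses the completed 4-year follow-up.

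For a full 12-subject trial cut between about 36 and 47 months, a little over half to under two-thirds of planned follow-up, and more than three-quarters at 75 Gy, comes after it. The dose groups are compared with mean follow-up differing about threefold and with no common 24-month estimate. That last statement is sensitive to accrual only slightly slower than the slowest schedule considered. Escalation after 0 of 3 DLTs, which the protocol's monitoring text allows although Number of Subjects does not, would shorten 60 Gy follow-up and raise the unanalysed share.

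BCR is secondary and descriptive, with no decision attached, and MTD determination is unaffected.

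**What to change.** Keep the planned analysis and label it preliminary. Add to the SAP a final Kaplan-Meier analysis of BCR, overall, by dose and by EBRT status, when the last subject completes the 4-year follow-up. Time it from prostatectomy, and report estimates at fixed times (for example 12, 24 and 48 months) with confidence intervals and numbers at risk.

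Reconcile the protocol's long-term schedule so that the PSA data exist: Table 1 against Table 2 and the PSA-at-each-visit statement, and six-monthly against yearly visits in the Follow-Up section.

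The cost is a short SAP addition, one rerun of the same analysis, and a final BCR result about 42 months after the preliminary one (78 − 36, or 89 − 47). It needs no extra subjects, and no visits beyond the 4-year follow-up once that schedule is settled. With at most 6 MTD-evaluable subjects per dose, the final estimates will remain imprecise and should be presented so.
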